### **6.1.3. Follow-up Process for Clarification of Information**

For critical data points (e.g., exposure and outcome data), if there are outstanding questions, discrepancies between forms, or missing data, the appropriate reporter will be contacted for clarification. If needed, 3 subsequent attempts will be made at intervals of approximately 2 weeks. If no further information is obtained, qualified program staff or the principal investigator will make a logical determination on discrepant information based on the available data. All clarifications and/or changes will be documented and traceable.

## **7. STUDY PARTICIPANT MANAGEMENT AND DISPOSITION**

### **7.1. Valid Versus Invalid Participants**

A valid participant is defined as an individual with sufficient data (i.e., the minimum criteria for enrollment; see Section 4.2) submitted to the surveillance program. Participants who lack the minimum data required for enrollment into the study will be considered invalid. Invalid participants will be enumerated in each surveillance program report but will not be included in the analysis population.

#### **7.1.1. Duplicate Reports**

With reports coming from multiple sources (i.e., pregnant or lactating individuals and HCPs), it is important to ensure that each case is counted only once [National Birth Defects Prevention Network (NBDPN) 2004]. Identification of duplicate reports may be problematic for the anonymously reported, de-identified cases where there is no specific identifying information. Reports received by the surveillance program will be reviewed for possible duplicate reporting. On receipt of a registration form, the report will be compared with other reports based on available data (e.g., age, LMP, EDD, and exposure information) to determine if the same report was received previously. If no duplication is identified, the report will be considered valid. If duplication is identified, the pregnancy reported earliest or the one with the most complete data will be maintained as the valid pregnancy and updated with any data from the other report not already captured. The duplicate report will be considered invalid, with the reason being “duplicate report.”

### **7.2. Prospectively Enrolled Versus Retrospectively Enrolled Participants**

The surveillance program will encourage prospective enrollment; however, retrospective enrollment in the surveillance program will be permitted. For participants exposed to omaveloxolone during both pregnancy and lactation, a prospectively enrolled participant is defined as an individual who is enrolled or for whom initial contact with the surveillance program is made prior to pregnancy outcome. For participants exposed during lactation only, data will be reported separately from pregnancy exposure cases and a prospectively enrolled participant is defined as an individual who is enrolled prior to the start of breastfeeding. For participants exposed to omaveloxolone during both pregnancy and lactation, a retrospectively enrolled participant is defined as an individual who is enrolled or for whom initial contact with the surveillance program is made after the pregnancy outcome has occurred. For participants exposed during lactation only, data will be reported separately from pregnancy exposure cases and a retrospectively enrolled participant is defined as an individual who is enrolled following the start of breastfeeding. Retrospectively enrolled participants can be biased toward the reporting of more unusual and severe outcomes and are less likely to be representative of the general population than prospectively enrolled participants. Retrospectively enrolled participants and participants exposed during lactation only will be excluded from the analysis population and summarized separately in reports (see Section 9.2.1 and Section 9.2.2).

Diagnostic prenatal tests (e.g., ultrasound to scan for structural defects at approximately 20 gestational weeks, chorionic villus sampling, and amniocentesis) can determine with high accuracy whether a fetus has a structural or chromosomal abnormality. If the results of

diagnostic prenatal testing are known prior to enrollment or first contact with the surveillance program, regardless of the results, the individual will be considered prospectively enrolled. However, this practice may introduce bias due to knowledge or perceived knowledge (through diagnostic prenatal testing) of the pregnancy outcome [Gliklich 2020; Kennedy 2004]. If the sample size allows, 3 groups of prospectively enrolled participants will be examined in supplementary analyses:

- Individuals who are enrolled or for whom initial contact with the surveillance program is made prior to pregnancy outcome and prior to diagnostic prenatal testing (true prospective subgroup)
- Individuals who are enrolled or for whom initial contact with the surveillance program is made prior to pregnancy outcome but after diagnostic prenatal testing that did not indicate a fetal abnormality
- Individuals who were enrolled or for whom initial contact with the surveillance program is made prior to pregnancy outcome but after diagnostic prenatal testing that indicated a fetal abnormality

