#### **4.2.1. Inclusion Criteria**

Each individual must meet the following inclusion criteria to be eligible for this study:

- Exposure to at least 1 dose of omaveloxolone per label for FA at any time during pregnancy (from 12 days prior to conception to pregnancy outcome) and/or at any time during lactation (up to 1 year of infant age or weaning, whichever comes first).

- Informed consent or IRB-/EC-approved waiver of informed consent.

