#### **4.2.3. Enrollment Criteria**

The minimum criteria required for enrollment into the surveillance program are:

- Sufficient evidence to confirm that the individual is exposed to at least 1 dose of omaveloxolone per label for FA at any time during pregnancy or lactation
- Sufficient information to determine whether the participant is prospectively or retrospectively enrolled (i.e., whether the outcome of pregnancy occurred prior to first contact with the surveillance program)
- Full contact information for the reporter who enrolls the participant (i.e., pregnant or lactating individual, or HCP) to allow for follow-up

Participants without the minimum criteria for enrollment will be considered invalid and will not be included in the analysis population.

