## **8. DEFINITIONS OF VARIABLES**

### **8.1. Exposure Definitions and Ascertainment**

Exposure to omaveloxolone is a condition for enrollment. Exposure is defined as bodily uptake of at least 1 dose of omaveloxolone at any time during pregnancy (from conception to pregnancy outcome), prior to pregnancy (within a specified time based on the product's half-life), or during lactation. Due to the 57-hour half-life of omaveloxolone, participants will be considered exposed during pregnancy if a dose is taken within 12 days (5 half-lives) prior to conception. Participants will be considered exposed during lactation if a dose is taken at any time during lactation.

Detailed information on dose, route, frequency, dates/duration of exposure, and indication/reason for use will be collected, and exposure will be further categorized by earliest trimester of exposure. For information on the methods used to determine gestational age and trimester of exposure, refer to Section 8.3. Exposure information will be updated at each pregnancy and infant follow-up.

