#### **9.2.1. Demographic and Baseline Characteristics**

Demographic and baseline characteristics will be summarized with simple descriptive statistics and presented in tables and listings. Demographic and baseline characteristics will be summarized for the entire enrolled population cumulatively and stratified by the following sub-populations, which are not mutually exclusive:

- Analysis population (see Section 7.7)
- Participants prospectively enrolled in the lactation only study
- Retrospectively enrolled participants
- Prospectively enrolled participants lost to follow-up
- Participants with only patient-reported data

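### Section 7.2 makes prospective status practically unattainable for lactation-only participants, so a planned sub-population is empty or nearly so and almost every lactation-only case is labeled retrospective

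*Protocol*

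**What the plan says.** All references are to the Protocol.

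- **Section 7.2** gives lactation-only participants their own rule. On one side, "a prospectively enrolled participant is defined as an individual who is enrolled prior to the start of breastfeeding"; on the other, "a retrospectively enrolled participant is defined as an individual who is enrolled following the start of breastfeeding". Only enrollment counts here. The rule for pregnancy exposure also accepts initial contact with the program, but the lactation-only rule does not.
- **Section 8.1** states: "Exposure to omaveloxolone is a condition for enrollment". It adds: "Participants will be considered exposed during lactation if a dose is taken at any time during lactation".
- **Section 4.2.3** lists among the minimum criteria "Sufficient evidence to confirm that the individual is exposed to at least 1 dose of omaveloxolone per label for FA", and treats anyone who lacks them as invalid.
- **Section 4.2.1** sets the pregnancy window from 12 days before conception to the pregnancy outcome. It says when the lactation window closes (1 year of infant age or weaning) but not when it opens.
- **Section 9.2.1**, and the synopsis with the same line, plans baseline summaries for "Participants prospectively enrolled in the lactation only study".
- **Sections 4.2.3 and 7.7** use a different test of prospective status: whether the pregnancy outcome came before first contact. Section 7.7 places all lactation-only participants among those whose outcome came first.

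**The concern.** Exposure has to come before enrollment, and a lactation-only exposure has to come after lactation has begun. A rule that calls such a woman prospective only if she enrolled before breastfeeding asks for an order of events that the eligibility rules exclude.

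Two things are at stake. First, the protocol commits to a baseline sub-population that cannot be filled in practice. Second, the label carries meaning: section 7.2 warns that retrospective participants may over-represent unusual and severe outcomes. That warning fits a mother who reports because her infant fell ill. It does not fit a mother who enrolls while her infant is well and is followed to 1 year. Under 7.2 both get the same label, so a reader of the lactation-only infant outcomes cannot tell them apart. Infant outcomes after exposure through breastfeeding are part of the objective in section 2.1.

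**Working it through.** No sample size, power or error rate enters here, and the protocol gives no figure to reproduce. The check is one of time order.

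**Events.** D = first qualifying dose; E = enrollment (date of consent, or of the completed form under a waiver, section 6.1.1.1); B = start of breastfeeding.

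**Conditions.**
1. Eligibility (4.2.3, 8.1): exposure is confirmed by enrollment, so D ≤ E.
2. Lactation-only (4.2.1, 8.1): there is no dose from 12 days before conception to the pregnancy outcome, so D falls in lactation. If lactation starts with breastfeeding, B ≤ D.
3. Prospective (7.2): E < B.

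**Combined:** D ≤ E < B ≤ D, which is impossible.

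**Count of orderings.** Three events have 3! = 6 strict orderings. Condition 1 leaves three: D-E-B, D-B-E and B-D-E. Condition 2 leaves one: B-D-E. Section 7.2 classes that ordering as retrospective. Same-day ties of D and E change nothing, because B ≤ D = E still rules out E < B.

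**The other reading of lactation.** Suppose lactation starts at delivery, L, before the first breastfeed. Condition 2 becomes L ≤ D, and L ≤ D ≤ E < B can be met. Dose, confirmation of exposure and consent must then all fall between delivery and the first breastfeed. The stratum is practically empty rather than strictly empty.

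**A case on which the sections disagree.** A woman contacts the program while pregnant and unexposed, then takes a first dose and enrolls while breastfeeding.

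| Section | Test | Result |
|---|---|---|
| 4.2.3 | Pregnancy outcome before first contact? | No, so prospective |
| 7.2 | Enrolled before breastfeeding? | No, so retrospective |
| 7.7 | Lactation-only assumed to have outcome before first contact | The description does not fit her |

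**Size.** Prospective lactation-only participants: 0 on the first reading, close to 0 on the second. Retrospective: all, or nearly all. The protocol expects 10 to 20 participants in total and does not say how many will be lactation-only, so the number affected could lie anywhere from none up to that total.

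**The case against.** The strongest reply is that little depends on the label. Lactation-only participants are outside the analysis population however they are classed (7.2, 7.7, 9.2.2), and no outcome summary is planned by prospective status within that group. This stands, and it limits the point to one baseline stratum and to interpretation.

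Four stronger readings are tempting, and the protocol does not support them.

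- *The stratum is exactly zero by construction.* This needs lactation to begin when breastfeeding begins. The start of lactation is not defined, so the text supports empty or practically empty, and no more.
- *Lactation-only outcomes will be pooled with retrospective pregnancy exposures.* Sections 3.1, 7.2 and 9.2.2 promise separate reporting, and 9.2.2 lists lactation-only participants as a supplementary group of their own. What remains is untidiness. The sub-populations in 9.2.1 may overlap, the retrospective group is nowhere limited to pregnancy exposures, and the report contents in 13.5 name no lactation-only group.
- *Pregnancy-only exposure, and so every fetal loss, is left unclassified.* The sentence in 7.2 does begin "For participants exposed to omaveloxolone during both pregnancy and lactation, a prospectively enrolled participant is defined as an individual". But the first-contact test in 4.2.3 and 7.7 covers any pregnancy exposure, and section 3.2 expressly provides for fetal loss among prospectively enrolled individuals. The wording in 7.2 is loose, but no case goes unclassified.
- *A woman who made contact before the outcome but enrolled after it meets both pregnancy definitions.* Taken alone, 7.2 allows this. The first-contact test in 4.2.3 and 7.7 settles it as prospective.

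**Conclusion.** The point holds within limits. The lactation-only rule in 7.2 cannot separate cases enrolled ahead of the infant's outcomes from cases reported because of them, since the eligibility rules put essentially every case on one side. The sub-population planned in the synopsis and 9.2.1 will be empty or practically empty, and 7.2, 4.2.3 and 7.7 do not share one test.

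The consequence is confined to that baseline stratum and to the labeling and reading of lactation-only infant outcomes. The analysis population, the Table 3 rates calculated in it and the primary malformation estimate are untouched. The conclusion rests on two assumptions: that exposure must be confirmed by the time of enrollment, as 4.2.3 and 8.1 state, and that lactation starts no earlier than delivery. It is worth correcting because a stated rule cannot do its job and the repair is cheap.

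**What to change.** 1. **Section 7.2, lactation-only.** Class a participant as prospective if first contact or enrollment comes before the occurrence or knowledge of any infant outcome that can arise after the first lactation exposure: postnatal growth deficiency, developmental delay, serious or opportunistic infection, hospitalization due to serious illness, or infant death. Class everyone else as retrospective, so that the two groups are complementary. Do not count outcomes fixed at birth (preterm birth, SGA, malformations). They precede any lactation-only exposure, and counting them would make the mother of every preterm or SGA infant retrospective for a reason unrelated to the drug in milk.
2. **Section 9.2.2.** Split the lactation-only summary by this definition.
3. **Sections 9.2.1, 9.2.2 and 13.5.** State that the retrospectively enrolled group means pregnancy exposures only, and that lactation-only cases are a separate group.
4. **Section 7.2, pregnancy.** Replace the restriction to women exposed in both periods with any pregnancy exposure, and use the first-contact test of 4.2.3 and 7.7. Make those two sections refer to the lactation-only rule.

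The cost is protocol wording. Section 6.1.1 already collects the dates of first contact, enrollment, breastfeeding start and stop, and infant death, and section 6.1 the completion date of each form. Infant illnesses and hospitalizations are listed without naming their dates, so check that the Infant Outcomes Form records them.

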### **7.3. Participants Lost to Follow-up**

A participant will be considered lost to follow-up if follow-up information is never obtained or is unavailable; pregnant individuals without pregnancy outcome information will be considered lost to follow-up, and live-born infants without follow-up data after birth will be considered lost to follow-up. See Section 6.1.2 for more information on the circumstances under which participants will be considered lost to follow-up. Participants who are lost to follow-up will be excluded from the analysis population, but their demographic and baseline characteristics will be summarized in the reports (see Section 9.2.1).

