### **Statistical Methods:**

The study population will include individuals who are exposed to at least 1 dose of omaveloxolone at any time during pregnancy (from 12 days prior to conception to pregnancy outcome) and/or lactation up through the first year following delivery.

The analysis population will include participants who:

- Are valid (i.e., meet the minimum criteria for enrollment [see Section 7.1] and are not a duplicate report)
- Are prospectively enrolled and were not exposed during lactation only
- Have HCP confirmation of data (i.e., do not have only patient-reported data)
- Have pregnancy outcome data or infant outcome data available (i.e., are not considered lost to follow-up)

This study is observational, and epidemiologic methods will be employed for data collection and analyses. Analyses will be conducted in accordance with the study objectives and applicable guidelines.

Study data will be summarized in tables and listings, as appropriate. These data include maternal demographic characteristics and pre-pregnancy anthropometrics, pregnancy information, maternal obstetrical history, family history of congenital malformations, disease information, maternal exposures during pregnancy, pregnancy outcome information (including gestational age of outcome), maternal lactation information and exposures during lactation (if applicable), and infant outcome information. For each continuous variable, the number of observations, median, mean, standard deviation, minimum, and maximum will be reported. For each categorical variable, the frequency and percentage in each category will be reported. The frequency and percentage of participants with missing data for each data point will be presented. Results will be rounded to 1 decimal place; therefore, percentages may not always add up to 100.

The incidence rates of the outcomes of interest in the analysis population will be calculated and reported. To put the surveillance program data into context, background rates from population-based surveillance systems and the published literature (e.g., Metropolitan Atlanta Congenital Defects Program [MACDP], National Vital Statistics System) will be referenced in the reports.

Demographic and baseline characteristics will be summarized for the entire enrolled population cumulatively and stratified by the following sub-populations, which are not mutually exclusive:

- Analysis population
- Participants prospectively enrolled in the lactation only study

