## 6. DATA COLLECTION

### 6.1. Data Collection Process

Enrolled individuals and the HCPs involved in their care or the care of their infants, if applicable, will serve as data reporters to the surveillance program. If the participant is enrolled by an HCP under an IRB-/EC-approved waiver of informed consent, the HCP who enrolled the participant will be responsible for providing all follow-up data to the surveillance program. It is anticipated that most obstetric data will be collected (directly or via the reporter who enrolled the participant) from the participant's obstetric HCP, defined as any HCP who provides care during pregnancy (e.g., obstetrician, family practitioner, general practitioner); it is anticipated that most pediatric and lactation data will be collected (directly or via the reporter who enrolled the participant) from the infant's pediatric HCP, defined as any HCP who provides pediatric care (e.g., pediatrician, family practitioner, general practitioner). The surveillance program may also request data from other HCPs involved in the individual's or infant's care (e.g., prescriber, specialist) after appropriate medical release is obtained from the individual.

The data collection process for each participant enrolled prior to pregnancy outcome will begin at enrollment, and cumulative data throughout the pregnancy will be collected: at enrollment, at the end of the second trimester (approximately 26 gestational weeks), at pregnancy outcome (live birth or fetal loss), and during lactation. For participants enrolled after pregnancy outcome, all available pregnancy data will be collected at enrollment. For live-born infants, data will be collected at 2 timepoints: approximately 4 months and 1 year after delivery. Data collection forms are described below and will be identical for all enrolled participants regardless of their method of enrollment. Reporters to the surveillance program will use the data collection forms and will be instructed to transcribe data that are readily available in the patients' medical records into the data collection forms. If data are collected via telephone by the VRCC, the VRCC will complete the data collection forms.

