Data related to congenital malformations will be solicited at all data collection timepoints (at enrollment and throughout pregnancy on the **Pregnancy Information Form**, which collects data on prenatal testing, at pregnancy outcome on the **Pregnancy Outcome Form**, and throughout the infant’s first year of life on the **Infant Outcomes Form**). If a congenital malformation (major or minor) or other event of interest is reported, additional information may be requested from the reporter on the **Targeted Follow-up Form** to properly characterize the event. Outcomes of pregnancies that meet serious adverse event (SAE) reporting requirements are included in Section 12.3.2. The date each data collection form is completed will also be collected. Table 1 provides a summary of the data collection process, including the forms that will be used to collect the data, the timing of the completion of each form, the potential reporters or sources of the data, and the types of data that will be collected. Section 6.1.1 provides further details regarding the data collected.

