| Minor congenital malformation       | An anomaly or abnormality of body structure that is present at birth, is of prenatal origin (i.e., birth defect), poses no significant health problem in the neonatal period, and tends to have limited social or cosmetic consequences for the affected individual [Centers for Disease Control and Prevention (CDC) 2020] | 
The surveillance program defines and codes minor congenital malformations with criteria specified as defined by CDC [Centers for Disease Control and Prevention (CDC) 2019]. The same process for adjudicating MCMs will be used to adjudicate minor congenital malformations.
   |

| Outcome                          | Definition  | Ascertainment  |
|----------------------------------|---|--|
| Gestational diabetes             | Any degree of glucose intolerance with onset or first recognition during pregnancy [ American Diabetes Association 2004 ]   | -  |
| Preeclampsia                     | High blood pressure and signs of liver or kidney damage (e.g., proteinuria) occurring at >20 gestational weeks [ ACOG Committee on Practice Bulletins--Obstetrics 2002 ]  | -  |
| Fetal loss                       | A fetal loss that occurs for any reason at any time during pregnancy  | -  |
| Spontaneous abortion (SAB)       | An involuntary fetal loss or the expulsion of the products of conception occurring at <20 gestational weeks   | Section 8.3 provides information on the methods used to calculate gestational age. |
| Stillbirth                       | As defined by the ACOG, an involuntary fetal loss occurring at $\geq 20$ gestational weeks or, if gestational age is unknown, a fetus weighing $\geq 350$ g [ American College of Obstetricians and Gynecologists (ACOG) 2020 ] | Section 8.3 provides information on the methods used to calculate gestational age. |
| Elective or therapeutic abortion | A voluntary fetal loss or interruption of pregnancy that occurs for any reason, including but not limited to for the preservation of maternal health or due to fetal abnormalities  | -  |
| Fetal loss, type not specified   | A fetal loss that is not reported as SAB, stillbirth, or elective therapeutic abortion  | -  |
| Live birth                       | The birth of a living fetus at $\geq 20$ gestational weeks or, if gestational age is unknown, weighing $\geq 350$ g   | -  |

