**Table 3. Calculation of Outcome Prevalence**

| Outcome                        | Numerator  | Denominator   |
|--------------------------------|--|---|
| Primary analysis        | Live births and stillbirths with confirmed MCMs ( including MCMs not associated with medication exposure) among individuals with pregnancy outcome data and exposure during the first trimester | Live births among individuals with pregnancy outcome data and exposure during the first trimester |
| Secondary analysis      | Live births and stillbirths with confirmed MCMs ( excluding MCMs not associated with medication exposure) among individuals with pregnancy outcome data and exposure during the first trimester | Live births among individuals with pregnancy outcome data and exposure during the first trimester |
| Minor congenital malformations | Live births with minor congenital malformations among individuals with pregnancy outcome data  | Live births among individuals with pregnancy outcome data   |
| Gestational diabetes           | Gestational diabetes among individuals with pregnancy outcome data   | Individuals with pregnancy outcome data   |
| Preeclampsia                   | Pre-eclampsia among individuals with pregnancy outcome data  | Individuals with pregnancy outcome data   |

| Outcome   | Numerator   | Denominator  |
|--|--|---|
| Fetal loss   | Fetal losses, including SABs, stillbirths, elective or therapeutic abortions, and losses with unknown type, among individuals with pregnancy outcome data                          | Individuals with pregnancy outcome data   |
| SAB  | SABs among individuals with pregnancy outcome data who are enrolled and exposed prior to 20 gestational weeks  | Individuals with pregnancy outcome data who are enrolled and exposed prior to 20 gestational weeks  |
| Stillbirth   | Stillbirths among individuals with pregnancy outcome data  | Live births and stillbirths among individuals with pregnancy outcome data   |
| Elective or therapeutic abortion                                   | Elective or therapeutic abortions among individuals with pregnancy outcome data  | Live births among individuals with pregnancy outcome data   |

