Because the surveillance program will enroll individuals only after recognition of pregnancy and in some cases much later in pregnancy, there will be left truncation of the enrolled population. That is, the enrolled population of pregnant individuals will include individuals with a shortened period at risk of the outcomes of interest and will exclude individuals who have already had certain outcomes (e.g., SAB, elective or therapeutic abortion). To minimize the impact of this potential bias, the surveillance program's recruitment strategy will encourage recruitment of participants as early in pregnancy as possible. Since the analysis of surveillance program data is

focused on prospective enrollment, misclassification of drug exposure is non-differential with regard to outcome. However, outcome misclassification could occur especially with regard to minor congenital malformations that may be overlooked or unreported. Although some malformations may not be easily visible at birth, most will be apparent by 1 year of age, so misclassification of these outcomes is expected to be minimal in this surveillance program, which aims to follow infants through 1 year of age.

Pregnancies that result in fetal losses (stillbirths, SABs, and elective or therapeutic abortions) without reported MCMs may introduce a classification bias. The percentage of these pregnancies consisting of potentially normal outcomes or MCMs is unknown. The surveillance program's data collection forms attempt to obtain information on MCMs detected via prenatal testing and at the time of the outcome. However, the reporting physician may not know the condition of the lost fetus.

Finally, it is possible that outcomes among pregnant individuals and infants who are lost to follow-up could differ from those with documented outcomes. Because of differences in individual reporting patterns, it is not possible to assess with any certainty what impact the potential biases from the losses to follow-up may have on the analysis. However, the characteristics of those participants considered lost to follow-up will be descriptively compared with those in the analysis population in an attempt to address this potential source of bias.

The combined impact that potential biases will have on the study results is unknown, but each source of potential bias will be examined and discussed in the reports.

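### The spontaneous abortion denominator drops women documented as still pregnant past 20 weeks and then lost, although they are known non-cases

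*Protocol*

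**What the plan says.** Section 7.3 makes the final outcome the test of follow-up: "pregnant individuals without pregnancy outcome information will be considered lost to follow-up". The consequence is in the same section: "Participants who are lost to follow-up will be excluded from the analysis population, but their demographic and baseline characteristics will be summarized". Section 7.7 repeats the exclusion when it defines the analysis population.

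Table 3 applies the same condition again in the SAB row, where both numerator and denominator are limited to "individuals with pregnancy outcome data who are enrolled and exposed prior to 20 gestational weeks".

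Table 2 defines SAB as "An involuntary fetal loss or the expulsion of the products of conception occurring at <20 gestational weeks". Section 6.1 schedules data collection at enrollment, at about 26 gestational weeks and at pregnancy outcome. Table 1 names the obstetric provider, or the enrolling provider for de-identified cases, as a source of the Pregnancy Information Form used at each of these points.

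The supplementary outcome summaries in Section 9.2.2 cover retrospective, patient-report-only and lactation-only participants. Prospective participants who are lost are not on that list. On their effect, Section 9.2.4 says "it is not possible to assess with any certainty what impact the potential biases from the losses to follow-up may have on the analysis".

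**The concern.** SAB status is settled at 20 weeks, but the plan asks for information from the end of pregnancy before it counts anyone. Between the two lies a scheduled provider form. A woman whose form shows an ongoing pregnancy at 26 weeks cannot have had an SAB in that pregnancy. If she is then lost, the plan treats her SAB status as unknown and removes her. A participant with a reported SAB has her outcome recorded and always stays in.

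Exclusion after documented passage of 20 weeks can therefore remove only non-cases. It raises the reported SAB proportion for a reason unrelated to the drug. The program expects about 10 to 20 participants and will set its rates beside background rates, so each wrongly dropped woman moves the figure visibly.

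The rule also departs from the plan's own practice. For infant outcomes assessed at several timepoints, Section 9.2.2.1 uses the infants who have data for that outcome at that timepoint. SAB is not handled by that principle.

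**Working it through.** **Inputs from the protocol**
- SAB window: before 20 gestational weeks (Table 2).
- Mid-pregnancy provider form: about 26 weeks (Section 6.1, Table 1).
- SAB denominator: outcome data required, enrolled and exposed before 20 weeks (Table 3).
- Anticipated enrollment: about 10 to 20 (Section 9.1). This is an expectation without a formula, so there is no figure of the plan to reproduce.

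**Assumptions.** The protocol gives no loss rate and no expected SAB count. Let N be the women enrolled and exposed before 20 weeks whose SAB status is known, x the SABs among them, and L those documented as pregnant at 20 weeks or later and then lost. The values below are illustrative.

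**Step 1: effect of a late loss.** Each one takes 1 from the denominator and 0 from the numerator.
- Under the protocol: x/(N−L).
- With documented status used: x/N.
- Ratio: N/(N−L), whatever the value of x.

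| N | x | L | Protocol | Late losses kept | Ratio |
|---|---|---|---|---|---|
| 10 | 2 | 2 | 2/8 = 25.0% | 2/10 = 20.0% | 1.25 |
| 12 | 2 | 1 | 2/11 = 18.2% | 2/12 = 16.7% | 1.09 |
| 12 | 2 | 3 | 2/9 = 22.2% | 2/12 = 16.7% | 1.33 |
| 20 | 3 | 1 | 3/19 = 15.8% | 3/20 = 15.0% | 1.05 |
| 20 | 3 | 3 | 3/17 = 17.6% | 3/20 = 15.0% | 1.18 |
| 20 | 3 | 4 | 3/16 = 18.8% | 3/20 = 15.0% | 1.25 |

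For 1 to 4 late losses the ratio runs from 20/19 = 1.05 to 20/16 = 1.25 at N = 20, and from 10/9 = 1.11 to 10/6 = 1.67 at N = 10.

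**Step 2: early losses.** Take 20 women enrolled and exposed before 20 weeks with a true SAB risk of 15%, so 3 expected SABs. Let 2 be lost before 20 weeks with unknown status and 2 be lost late. The protocol then divides by 20 − 4 = 16.
- Early losses at 15% risk: (3 − 2×0.15)/16 = 2.7/16 = 16.9%.
- Early losses at 30% risk: (3 − 2×0.30)/16 = 2.4/16 = 15.0%.

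Putting back only the two late losses gives 2.7/18 = 15.0% and 2.4/18 = 13.3%. In the first case the error is gone. In the second, the protocol's 15.0% was two opposite errors cancelling, and the remaining shortfall comes wholly from the early losses.

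**The case against.** **Net direction.** A reader might infer that the SAB rate as a whole is biased upward. The documents do not support that. Women lost before 20 weeks may have had unreported SABs, which pulls the rate down, and Step 2 shows that the two effects can cancel. As a statement about all losses together, the caution in Section 9.2.4 is therefore fair. It does not cover late losses, whose direction is known from forms already held.

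**Malformations.** A reader might also infer that malformations found prenatally in lost women vanish from the program. They do not. Under Table 2 the independent evaluator reviews every reported malformation, whatever its source. Sections 12.1.2 and 12.3.2 make malformations serious adverse events, sent to the sponsor within 24 hours of awareness, and Section 13.5 has the reports cover the data accumulated so far. Nor would changing Section 7.3 bring such a finding into the malformation rate. That rate counts affected live births and stillbirths over live births, and a fetus of unknown outcome fits neither. Adding only the affected lost cases would select on the event.

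**Gestational diabetes and preeclampsia.** These can arise after 26 weeks, so requiring a pregnancy outcome for them is defensible. Dropping late losses has no fixed direction here either. With 20 women, 2 recorded cases of gestational diabetes and 3 late losses, the protocol rate is 2/17 = 11.8% if no case is among the lost and 1/17 = 5.9% if one is.

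**Size.** The loss counts are assumed. The situation needs a provider who returns the 26-week form and then answers neither four contacts nor a final certified letter (Section 6.1.2). Anticipated enrollment also includes retrospective and lactation-only participants, so 12 or 20 women in this denominator is near or at the ceiling. The 95% interval around 2/12 is roughly 2% to 48%, and no hypothesis is tested. This limits the importance of the point but does not justify discarding a known status.

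**Left to the analysis plan.** The layout of listings can be. The SAB denominator cannot, because Table 3 fixes it.

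**Conclusion.** The point holds for the SAB denominator only. Requiring a final pregnancy outcome removes women already documented as past the SAB window and multiplies the reported proportion by N/(N−L). One late loss among 12 women with 2 SABs moves 16.7% to 18.2%, and three move it to 22.2%. The mechanism follows from the text alone. Its size rests on assumed counts, and it applies only to women enrolled and exposed before 20 weeks who have provider documentation at 20 weeks or later.

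The upward shift is certain for this component and not for the net rate. The handling of malformations, gestational diabetes and preeclampsia among lost participants is not shown to be wrong.

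**What to change.** In Sections 7.3 and 7.7 and the SAB row of Table 3, define the SAB denominator as prospective, provider-confirmed participants enrolled and exposed before 20 weeks who have either a pregnancy outcome or a provider-documented ongoing pregnancy at 20 weeks or later. Beside the rate, report the number lost before 20 weeks whose SAB status is unknown, so that the reader can see how much the early losses could matter.

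Optionally, list outside the rates any malformation, gestational diabetes or preeclampsia already recorded for participants lost later. Do not add these cases to the malformation or gestational diabetes numerators.

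The cost is a few lines of wording, one extra count and, if wanted, one listing. No new data are needed. The downside is that SAB will have a slightly different analysis set from the other outcomes, which a table footnote can explain.
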